# PROTOCOL SUMMARY

# SYNOPSIS

A) TRIAL IDENTIFICATION

SPONSOR – PROTOCOL CODE NUMBER: UC-GIG-1910

VERSION (NUMBER & DATE): version 3.0 dated 10 February 2022

**TRIAL TITLE:** A randomized, phase II study comparing the sequences of regorafenib and trifluridine/tipiracil, after failure of standard therapies in patients with metastatic colorectal cancer.

PHASE (FOR TRIALS ON MEDICINAL PRODUCTS): ||

ABBREVIATED TITLE: SOREGATT

INTERNATIONAL COORDINATING INVESTIGATOR: [name]

NUMBER OF CENTERS: 50 centers

NUMBER OF PATIENTS: 340 randomized patients

B) SPONSOR IDENTIFICATION					
NAME:	UNICANCER				
	[name]				
CONTACT PERSON:	[name], Project Manager				
	R&D UNICANCER, [contact] - email: [contact]				

### C) TRIAL GENERAL INFORMATION

**INDICATION:** The study population will consist of male and female patients aged  $\geq 18$  years old with metastatic colorectal cancer after failure of fluoropyrimidine-, irinotecan-, and oxaliplatin-based chemotherapies, as well as EGFR and VEGF inhibitors in patients eligible for these treatments.

**TRIAL DESCRIPTION/DESIGN:** Multicenter, international, comparative, randomized, open-label, phase II study conducted in two parallel groups.

**PRIMARY OBJECTIVE:** The primary objective will be to compare the feasibility of the treatment sequences, regorafenib then trifluridine/tipiracil (Arm A) and trifluridine/tipiracil then regorafenib (Arm B). The feasibility will be assessed in terms of percentage of patients able to receive both line of treatment.

G-

Protocol n°: UC-GIG-1910 - version n°3.0 – 10 February 2022

**SECONDARY OBJECTIVES:** The secondary objectives include the comparison between arms of:

- The Overall Survival (OS).
- The Progression-Free Survival in the first treatment line (PFS1).
- The Progression-Free Survival in the second treatment line (PFS2).
- The Disease control rate (DCR).
- The Objective response rate (ORR).
- The Time-to-treatment failure in the first treatment line (TTF1).
- The Time-to-treatment failure in the second treatment line (TTF2)
- The quality of life using patient reported outcomes: QLQ-C30 version 3.0
- The time to deterioration of ECOG PS  $\geq 2$
- The tolerance of the treatment sequences (by computing the incidence of adverse events using CTCAE v5.0).

#### **INCLUSION CRITERIA:**

The patient must meet all of the following inclusion criteria to be eligible for the study:

- 1. Patients must have provided informed consent before performing any study specific procedures.
- 2. Histological or cytological documented adenocarcinoma of the colon or rectum.
- 3. Patients with metastatic colorectal cancer (stage IV).
- 4. Measurable disease, defined as at least one unidimensional measurable lesion on a computed tomography (CT) scan according to RECIST v1.1.
- 5. The patient must have progressed following exposure of all the following agents: one fluoropyrimidine-based chemotherapy (capecitabine or fluorouracil [5-FU]), combined with oxaliplatin and/or irinotecan (including FOLFOX, FOLFIRI or FOLFOXIRI) as well as EGFR and/or VEGF inhibitors in patients eligible for these treatments.
- 6. Patients considered eligible for treatment with both regorafenib and trifluridine-tipiracil.
- 7. Male or female patients aged  $\geq 18$  years.
- 8. ECOG performance status of  $\leq 1$ .
- 9. Adequate bone marrow, liver and renal functions as assessed by the following laboratory requirements:
  - Total bilirubin  $\leq 1.5$  x upper limit of normal (ULN).

Protocol nº: UC-GIG-1910 - version nº3.0 – 10 February 2022

• Alanine aminotransferase (ALT) and aspartate aminotransferase (AST)  $\leq 2.5 \text{ x ULN}$  ( $\leq 5 \text{ x ULN}$  for patients with liver metastasis).

- Alkaline phosphatase limit  $\leq 2.5$  x ULN ( $\leq 5$  x ULN for patients with liver metastasis).
- Serum creatinine  $\leq 1.5$  x ULN.

• International normalized ratio (INR) and partial thromboplastin time (PTT)  $\leq$ 1.5 x ULN. Patients receiving anticoagulants, such as warfarin or heparin are eligible if there is no prior evidence of an underlying abnormality with coagulation.

• Platelet count  $\geq$ 75000 /mm3, hemoglobin (Hb)  $\geq$ 9 g/dL, absolute neutrophil count (ANC)  $\geq$ 1500/mm3. Blood transfusions to meet this inclusion criterion are not allowed.

- 10. Women of childbearing potential and men must agree to use a highly effective contraception (<1% failure rate) from the signing of the informed consent form until at least 6 months after the last study drug administration. Women using hormonal contraceptive must also use a barrier method.
- 11. Women of childbearing potential must have a negative pregnancy test within 7 days before starting study treatment.
- 12. Patients affiliated to the social security system
- 13. Patient willing and able to comply with the protocol for the duration of the study including treatment, scheduled visits, and examinations throughout the study, including follow up.

## **NON-INCLUSION CRITERIA:**

Patients who meet any of the following criteria at the time of screening will not be eligible for the study:

- 1. Patients with symptomatic brain or meningeal metastasis, unless definitive therapy occurred more than 6 months ago and with a confirmation of tumoral control within 4 weeks of starting study treatment.
- 2. Previous or concurrent cancer that is distinct in primary site or histology from colorectal cancer within 5 years prior to study inclusion, except for curatively treated in situ cervical cancer, non-melanoma skin cancer, and superficial bladder tumors: staged Ta (non-invasive tumor), Tis (carcinoma in situ), and T1 (tumor with lamina propria invasion).
- 3. Prior treatment with regorafenib or any other tyrosine kinase inhibitor.
- 4. Prior treatment with trifluridine/tipiracil.
- 5. Known hypersensitivity to any of the study drugs, study drug classes, or study drug excipients.
- 6. Unresolved toxicity grade >1 (by CTCAE v5.0) caused by prior therapy/procedure, excluding alopecia, hypothyroidism, and oxaliplatin-induced neurotoxicity grade  $\leq 2$ .
- 7. Patient with moderate or severe hepatic impairment (Child-Pugh C).
- 8. Known UGT1A1polymorphisms. History of Gilbert's syndrome.
- 9. Major surgical procedure, open biopsy, or significant traumatic injury within 28 days before starting study treatment.
- 10. Chemotherapy within 21 days of starting study treatment.

Protocol nº: UC-GIG-1910 - version nº3.0 – 10 February 2022

- 11. Radiotherapy within 4 weeks of starting study treatment, except for palliative radiotherapy within 2 weeks.
- 12. Active cardiac disease including any of the following:
  - Congestive heart failure: New York Heart Association (NYHA) class  $\geq 2$ .
  - Unstable angina (angina symptoms at rest), or a new-onset angina (within the 3 months before enrolment).
  - Myocardial infarction that occurred less than 6 months before enrolment.
  - Cardiac arrhythmias requiring anti-arrhythmic therapy (treatment with beta blockers or digoxin are permitted)
  - Uncontrolled hypertension despite optimal medical management.
- 13. Arterial or venous thrombotic or embolic events such as cerebrovascular accident (including transient ischemic attacks) within 6 months of starting study treatment. Deep vein thrombosis or active pulmonary embolism that are significant or not adequately controlled on anticoagulation regimen as per investigator's judgement.
- 14. Ongoing infection grade >2 (CTCAE v5.0).
- 15. Known history of human immunodeficiency virus (HIV) infection.
- 16. Active hepatitis B or C, or chronic hepatitis B or C requiring treatment with antiviral therapy.
- 17. Patients with seizure disorder requiring medication.
- 18. Patients with a history of any bleeding diathesis, irrespective of the severity.
- 19. Any hemorrhage or bleeding event grade  $\geq$ 3 (CTCAE v5.0) within the 4 weeks before starting study treatment.
- 20. Presence of a wound, ulcer, or bone fracture that is not healing.
- 21. Patients unable to swallow oral medications.
- 22. Bowel malabsorption or extended bowel resection that could affect the absorption of regorafenib, occlusive syndrome,
- 23. Presence of gastro-intestinal fistula or perforation
- 24. Any illness or medical conditions that are unstable or could jeopardize the safety of the patient and their compliance in the study.
- 25. Patients participating in another therapeutic study within the 30 days before enrolment.
- 26. Pregnant or breast feeding women.
- 27. Person deprived of their liberty or under protective custody or guardianship.

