## E) STATISTICAL ANALYSIS PLAN

#### **REQUIRED NUMBER OF PATIENTS TO BE SCREENED/INCLUDED:**

The primary endpoint is the feasibility of the treatment sequence. The hypothesis for the sample size calculation are based on the data published by Moriwaki et.al showing that 50% of the subjects receiving trifluridine/tipiracil were able to receive further treatment as compared to 65% with regorafenib (Moriwaki, Fukuoka et al. 2018). With a Chi-square test between the two arms, a bilateral type I error rate of 5% and a power of 80%, 170 patients are required in each arm, i.e. 340 patients in total.

E

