#### Primary endpoint analysis

The feasibility of the treatment sequence is defined as the percentage of patients who receive at least two cycles of both treatments in each arm, i.e. percentage of patients being treated until the first tumor evaluation. Thus, patients in Arm A, allocated regorafenib then trifluridine/tipiracil, will be considered a success if they received at least two cycles of regorafenib and two cycles of trifluridine/tipiracil. Similarly, patients in Arm B, allocated trifluridine/tipiracil then regorafenib, will be considered a success if they receive at least two cycles of trifluridine/tipiracil and two cycles of regorafenib.

Whenever the patient did not receive the second treatment (i.e toxicity, death, lost to follow-up...), it will be considered as a failure.

The comparison between the two trial arms will be adjusted for the stratification factors with a logistic regression model according to the intent-to-treat principle.

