# SCHEDULE OF VISITS AND ACTIVITIES (SOA)

VISITS	Baseline visit(s)	Visits during first treatment phase	Change of study treatment visit	Visits during the second treatment phase	Study treatment discontinuation visit	Long-term follow-up visits
Visit timelines	≤28 days before starting treatment	On D1 of each 28- day treatment cycle	≤4 weeks delay between first and second treatment phases	On D1 of each 28-day treatment cycle	30±7 days after second treatment discontinuation	Every 3±1 months for 3 years and every 6±1 months for 2 years
DRUG DISPENSING AND ACCOUNTABILITY		Х		Х		
Eligibility criteria	Х					
Signed informed consent form	X					
Randomization	Х					
PHYSICAL EXAMINATION	I				I	L
Assessment of all systems, vital signs (pulse and blood pressure), weight, and height a .	X 	Хр	X	Xp	X	Xc
ECOG PS	X 	X	X	X	X	Xc
Medical history	X					
Safety/toxicity (graded by CTCAE v5.0)	X	X	X	X	X	
Concomitant treatments	X	X	Х	Х	X	Xc
PARACLINICAL EXAMINATION	1					
Tumor assessment (CT scan by RECIST v1.1) d	X	X	X	X	X	
Electrocardiogram (12-lead)	X					
BIOLOGICAL TESTS						
Complete blood count with differential	X 	X	X 	X	X	
Blood electrolytes: sodium, potassium, chloride, calcium, and phosphate)	X 	Х	X 	X	Х	
Liver function tests: AST, ALT, bilirubin (total and direct), alkaline phosphatase, and GGT	X 	Xe	X 	Xe	Х	
Kidney function tests: creatinine (serum), and uric acid. Creatinine clearance estimated by Cockcroft-Gault equation.	X 	x	X 	X	X	
Proteinuria	X 	Х	X 	Х		
Pancreas function test: lipase, amylase	X 	Х	X 	Х	X	
Thyroid function tests: TSH, T3, and T4	X 	Х	X 	Х	X	
Coagulation panel: PT, INR, and PTT	X 	Х	X 	Х	Х	
Pregnancy test (urine or serum)	X 					

Protocol n°: UC-GIG-1910 - version n°3.0 – 10 February 2022

**G** 

VISITS	Baseline visit(s)	Visits during first treatment phase	Change of study treatment visit	Visits during the second treatment phase	Study treatment discontinuation visit	Long-term follow-up visits

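### Non-inclusion criterion 7 names two grades of hepatic impairment but only one Child-Pugh class, leaving class B unsettled

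*Protocol*

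**What the plan says.** In the Protocol's non-inclusion criteria, meeting any one item makes a patient ineligible. Item 7 reads "Patient with moderate or severe hepatic impairment (Child-Pugh C" (the bracket closes after the C). It is the only place in the document that mentions Child-Pugh, and no other text defines moderate impairment.

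Three other rules bear on liver function or general fitness:

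- Inclusion criterion 9 requires "Adequate bone marrow, liver and renal functions as assessed by the following laboratory requirements", followed by limits for bilirubin, ALT/AST, alkaline phosphatase, creatinine, INR/PTT and blood counts. ALT/AST and alkaline phosphatase have wider limits when there are liver metastases.
- Inclusion criterion 6 admits "Patients considered eligible for treatment with both regorafenib and trifluridine-tipiracil".
- Non-inclusion criterion 24 bars "Any illness or medical conditions that are unstable or could jeopardize the safety of the patient and their compliance in the study".

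Both arms plan regorafenib, first in Arm A and second in Arm B. The schedule of visits (footnote e) asks for liver tests every 2 weeks while it is given.

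**The concern.** The words and the bracket of one criterion do not match. A centre that follows the words excludes a patient with moderate impairment. A centre that takes the bracket as the working definition looks only for class C and may randomise the same patient.

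Safety comes first. The criterion decides whether patients with moderately impaired livers receive two drugs in sequence, and the extra liver tests show that the Protocol itself treats the liver as a concern under regorafenib. Consistency comes second: an eligibility rule applied across 50 centres should give the same answer for the same patient.

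**Working it through.** No figure in the plan needs reproducing. The check asks whether the text of criterion 7, or any other rule, settles the status of class B.

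**Step 1: possible readings of criterion 7.** Assumed convention, not in the Protocol: A mild, B moderate, C severe.

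| Reading | Class B patient |
|---|---|
| The words govern | Excluded |
| The bracket qualifies only the severe grade | Excluded, but moderate has no class attached |
| The bracket defines the whole phrase | Not excluded |

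The mismatch does not depend on the convention: two grades are paired with one class.

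**Step 2: does inclusion criterion 9 make the question moot?** Assumed scale, not in the Protocol: five items (bilirubin, INR, albumin, ascites, encephalopathy), each scored 1 to 3; A = 5–6, B = 7–9, C = 10–15. Take a patient within the limits of criterion 9, with bilirubin and INR each scoring 1, and with no encephalopathy (1). Ascites and albumin are not limited by criterion 9.

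- Both intermediate: 1 + 1 + 1 + 2 + 2 = 7, class B.
- Both at the worst score: 1 + 1 + 1 + 3 + 3 = 9, still class B.

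So a patient who meets the laboratory limits can be class B, and the question stays open.

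**Step 3: do the general clauses settle it?** Inclusion criterion 6 and non-inclusion criterion 24 give no hepatic class and leave the decision to the investigator. Inclusion criterion 8 (ECOG 0 or 1) makes marked ascites or encephalopathy less likely but sets no hepatic rule.

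**Step 4: which reading was probably meant?** In Step 2 the highest total without encephalopathy is 9, one short of class C. A bracket read as the whole definition would therefore bar almost nobody whom criterion 9 admits, and would make the word *moderate* redundant. This favours the words. It is not absolute: INR may score higher in some patients, notably since "Patients receiving anticoagulants, such as warfarin or heparin are eligible if there is no prior evidence of an underlying abnormality with coagulation".

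**The case against.** The strongest reply is that the operative words already exclude moderate impairment and that the bracket may belong only to the severe grade. The criterion would then be incomplete rather than contradictory. This is a fair reading, and Step 4 supports it as the likely intent. It still leaves moderate without a class, and it does not stop a centre from taking the bracket as the definition. It also points to the same correction.

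A second reply is that few patients are involved. That is probably right: ECOG 0 or 1, the laboratory limits and the investigator's judgement all narrow entry. It reduces the size of the problem but does not settle who is eligible.

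Two stronger inferences are tempting, and the document supports neither.

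- *A reader might infer that opposite decisions would both comply, so that monitoring could fault neither.* A patient with moderate impairment who is randomised breaches the literal words, and a monitor could cite them.
- *A reader might infer a predictable loss of power, because a patient who does not reach the second drug counts against the arm:* "Whenever the patient did not receive the second treatment (i.e toxicity, death, lost to follow-up...), it will be considered as a failure". Let a share f of patients be class B, with success rates a in Arm A and b in Arm B, and let the other patients succeed at the planned 65% and 50%. The difference is then 15(1 − f) + f(a − b) points. It falls if a − b is below 15 points and rises if it is above. The document gives none of f, a or b. The planned rates rest on published data, "50% of the subjects receiving trifluridine/tipiracil were able to receive further treatment as compared to 65% with regorafenib", and the class B share behind those data is not stated either. No size or direction can be claimed.

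**Conclusion.** The point holds as an internal inconsistency in an operative eligibility rule. Criterion 7 excludes two grades in words and names one class in its bracket, and nothing else in the document says whether class B is excluded. The case rests on patient safety and on uniform eligibility across centres. Sample size and the method of the primary analysis are not affected.

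The number of patients concerned is unknown and probably small. The conclusion assumes the usual mapping of grades to classes and, for the worked scores, the usual scoring. The mismatch itself needs neither.

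One limit remains. The text is headed as a protocol summary, and its regorafenib dosing section refers to recommendations set out in the protocol, so fuller wording may exist. Even if that wording is correct, the summary should agree with it.

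**What to change.** Change the bracket so that criterion 7 covers *moderate or severe hepatic impairment (Child-Pugh B or C)*. This keeps the words, completes the bracket and is the cautious choice. Only if the sponsor confirms that class B was meant to be eligible, write *severe hepatic impairment (Child-Pugh C)* instead. Check the same criterion in the full protocol and align the two texts in the next amendment.

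The cost is two added words and a few more screen failures, since class B patients whom some centres might now accept would be turned away. No visit is added, and sample size and analysis stay as they are. Scoring Child-Pugh requires albumin, which the schedule's liver row does not itemise ("Liver function tests: AST, ALT, bilirubin (total and direct), alkaline phosphatase, and GGT"); centres can obtain it as part of the baseline eligibility check.

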### PRIMARY ENDPOINT:

The primary endpoint is the feasibility of the treatment sequence defined as the percentage of subjects who receive at least two cycles of both regorafenib and trifluridine/tipiracil in each arm. Subjects will be

G-

Protocol n°: UC-GIG-1910 - version n°3.0 – 10 February 2022

considered as a success if they are administered at least two cycles of each line of therapy, i.e. percentage of patients being treated until the first tumor evaluation.

#### SECONDARY ENDPOINTS:

- Overall Survival (OS) is defined as the time interval from randomization until death from any cause.
- Progression-free survival 1 (PFS1) is defined as the time interval from randomization until death or the disease progression observed in the first sequence of treatment in each arm, evaluated using RECIST v1.1.
- Progression-free survival 2 (PFS2) is defined as the time interval from randomization until death or the disease progression is observed in the later sequence of treatment in each arm, evaluated using RECIST v1.1.
- Disease control rate (DCR) is defined as percentage of patients with a best response that is not progressive disease (PD) (either complete response [CR], partial response [PR], or stable disease [SD]) during treatment. DCR will be assessed in each study arm
- Objective response rate (ORR) is defined as percentage of patients with a best response being either complete response [CR] or partial response [PR] during treatment. ORR will be assessed in each study arm.
- Time-to-treatment failure 1 (TTF1) is defined as the time from randomization to treatment discontinuation for any reason (including disease progression, treatment toxicity, patient preference, or death) during the first sequence of treatment in each arm.
- Time-to-treatment failure 2 (TTF2) is defined as the time from randomization to treatment discontinuation for any reason (including disease progression, treatment toxicity, patient preference, or death) during the second sequence of treatment in each arm.
- Quality of life data using the patient reported outcomes, QLQ-C30 version 3.0 will be collected during the study.
- The time to ECOG PS ≥2 deterioration is defined as the time interval between randomization and the first documented ECOG PS ≥2 during the study.
- Data concerning adverse events graded using the CTCAE v5.0 will be collected during the study.

These endpoints will be compared between the study arms.

D) INVESTIGATIONAL MEDICINAL PRODUCTS								
PRODUCT NAMES AND ADMINISTRATION:								
Drug name (INN)	Registered name 	Pharmaceutical form	Administration route		Posology			
Regorafenib		40 mg film-coated tablets	d Per os		foll cyc Dur 80n day	
 
160 mg per day during 3 weeks
 
followed by 1 week off of each 4-week
 
cycle except for cycle 1.
 
During first cycle: dose is started at
 
80mg per day at week 1, 120mg per
 
day at week 2, 160mg per day at week
 
3, followed by 1 week off.
 
		
Drug name (INN)	Registered name 	Pharmaceutical form		Administration route		Posology		
Trifluridine/		- 15 mg/6.14 mg r	mg Pe	er os		35 mg/m 		

I riffuridine/	- 15 mg/6.14 mg mg	g Per os	35 mg/m 
tipiracil	film-coated tablets		Dose administered orally twice
	- 20 mg/8.19 mg film	-	daily on Days 1 to 5 and Days 8 to
	coated tablets		12 of each 4-week cycle.

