### THERAPEUTIC REGIMENS:

Patients will be randomized according to a 1:1 ratio to treatment arms A and B.

- Arm A: regorafenib until disease progression or unacceptable toxicity occurs, followed by trifluridine/tipiracil until disease progression or unacceptable toxicity occurs.
- Arm B: trifluridine/tipiracil until disease progression or unacceptable toxicity occurs, followed by regorafenib until disease progression or unacceptable toxicity occurs.

Prior to randomization, they will be stratified according to:

- Country
- ECOG (0 or 1)
- Age (<65 years old or  $\geq$ 65 years old)

The time span between the end of the first treatment phase and the initiation of second treatment phase should not exceed 4 weeks.

Protocol nº: UC-GIG-1910 - version nº3.0 – 10 February 2022

Page 6/12

The posology of regorafenib will be as follows: 80mg per day on C1W1, 120mg per day on C1W2, 160mg per day on C1W3, 1 week off (this 4-week period is considered a treatment cycle), followed by regorafenib 160 mg starting from cycle 2.

If a dose is missed, then it should be taken on the same day as soon as the patient remembers. The subject should not take two doses on the same day to make up for a missed dose. In case of vomiting after regorafenib administration, the subject should not take additional tablets.

The starting dose of trifluridine/tipiracil is 35 mg/  $m^2$ /dose administered orally twice daily on Days 1 to 5 and Days 8 to 12 of each 28-day cycle. The dosage is calculated according to body surface area. The dosage must not exceed 80 mg/dose

If doses are missed or held, the subject must not make up for missed doses.

Posology adjustments

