#### STATISTICAL ANALYSIS:

#### **Study population**

The following populations will be considered:

- Intent-to-Treat (ITT) population will include all randomized patients according to their randomized arm. This population will be used for the analysis of all efficacy endpoints.
- The safety population will include all the patients who have received at least one dose of either drug regardless of treatment period. This population will be used for the safety analysis.

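### As worded, TTF2 gives no event to a randomized patient who never starts the second drug, which tilts the between-arm comparison towards the sequence that fewer patients complete

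*Protocol*

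**What the plan says.** The protocol synopsis, under Secondary Endpoints, starts TTF2 at randomization and ends it at treatment "discontinuation for any reason (including disease progression, treatment toxicity, patient preference, or death) during the second sequence of treatment in each arm". Death is one of the listed reasons, so it falls under the same restriction to the second sequence. The list closes with "These endpoints will be compared between the study arms".

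The Study population section defines the ITT population as all randomized patients and adds: "This population will be used for the analysis of all efficacy endpoints".

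A rule for patients who never reach the second drug appears only under Primary endpoint analysis: "Whenever the patient did not receive the second treatment (i.e toxicity, death, lost to follow-up...), it will be considered as a failure". Nothing extends it to TTF2.

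The sample-size section plans on "50% of the subjects receiving trifluridine/tipiracil were able to receive further treatment as compared to 65% with regorafenib".

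**The concern.** TTF2 starts its clock for everyone, but only patients who start the second drug can have its event. For someone who stops the first drug through toxicity, decline or death and goes no further, the sequence has failed outright. The primary analysis says so, yet under the TTF2 wording the same patient is event-free.

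Such patients have to be censored somewhere, and that censoring is informative because of why they stopped. It is also unequal by design, since the trial expects more patients to go on to further treatment after regorafenib (Arm A) than after trifluridine/tipiracil (Arm B). The arm in which more patients reach the second drug collects more TTF2 events and looks worse on TTF2 for that reason alone. A secondary endpoint could then appear to contradict the primary one through its definition.

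**Working it through.** **The plan's own figure.** With 50% versus 65%, a chi-square test with pooled variance and no continuity correction, two-sided 5% and 80% power, the requirement is 170 per arm (power at 170: 80.2%). This matches the protocol and is not in dispute. The protocol states no figure for TTF2.

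**How many patients.** The protocol gives no rate of never starting the second drug. Taking the planning rates as start rates (assumption):
- Arm A: 170 × (1 − 0.65) = 59.5, about 60.
- Arm B: 170 × (1 − 0.50) = 85.
- Together about 145 of 340 (43%).

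These are upper figures. The protocol also uses 65% and 50% as planning values for at least two cycles of both drugs. If those are the success rates, start rates are at least that high and never-starters are fewer.

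**Direction.** Let *p* be the share starting drug 2. For starters, let *g(t)* be the density and *S(t)* the survivor function of time to stopping drug 2. Let *C(t)* be the share of never-starters not yet censored at *t*. Take *g*, *S* and *C* as the same in both arms. Leaving aside administrative censoring common to the arms, the hazard that the analysis sees is

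p·g(t) / [p·S(t) + (1 − p)·C(t)] = g(t) / [S(t) + ((1 − p)/p)·C(t)].

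This rises with *p* whenever C(t) > 0. At 65% and 50%, (1 − p)/p is 0.35/0.65 = 0.54 in Arm A and 0.50/0.50 = 1.00 in Arm B. The hazard is therefore higher in Arm A for any common censoring date.

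If never-starters count as failures when drug 1 stops, the survivor function is p·S(t) + (1 − p)·S₁(t), where S₁ refers to time on drug 1. If drug-1 time does not depend on later starting, S ≥ S₁, because starters add the gap and drug 2. The arm with larger *p* then does better.

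**Size, by simulation.** Assumptions not in the protocol: exponential durations with 2-month medians for each drug, identical in both arms; a 0.5-month gap; median 3 months from stopping drug 1 to death in never-starters. Accrual is uniform over 2 years with cutoff at 3 years, in line with the stated trial durations. Only the start rates differ between arms. A hazard ratio above 1 favours Arm B. Ranges are over repeated runs.

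| Never-starters handled as | HR A/B, 65% vs 50% start | HR A/B, 80% vs 70% start |
|---|---|---|
| Censored when drug 1 stops | 1.11–1.13 | 1.04–1.07 |
| Censored at death | 1.32–1.34 | 1.15–1.17 |
| Event-free to cutoff | 1.47–1.48 | 1.28–1.30 |
| Counted as failures when drug 1 stops | 0.88–0.90 | 0.93–0.94 |

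The 80% versus 70% column is an assumed milder case. At 65% versus 50%, with medians of 2 or 3 months per drug and 3 or 6 months to death, the rows give 1.11–1.15, 1.32–1.39, 1.44–1.48 and 0.88–0.90. Over the same settings, nominal p < 0.05 occurred in about 9–16%, 43–61% and 72–79% of simulated 340-patient trials under the three censoring rules, with no true difference in drug durations.

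**The case against.** **Censoring belongs to the SAP.** The protocol states no censoring rule for TTF2, a SAP not shown may supply one, and the size of the effect depends on it. This stands for the size. It does not remove the point: a SAP can choose a censoring date, but turning never-starters into events would change the protocol's event definition.

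**The phrase may only separate TTF2 from TTF1.** The two definitions are worded alike. Even so, a patient who never started the second treatment cannot discontinue it, so the gap remains. Two readings make the tilt largely vanish: dropping never-starters (HR about 1.0), or treating every death as an event (about 1.02–1.04). The first conflicts with the ITT rule, and the second is not what the definition says.

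**The never-start rates are not in the protocol.** A reader might infer that 35% and 50% never start the second drug. The protocol does not support this as fact. The rates concern further treatment, without saying that it was the other study drug, and they also serve as planning values for two cycles of both drugs. This objection stands.

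**The simulated durations do not match the planning hypothesis.** With a 2-month exponential median, the share still on a drug at 56 days is exp(−0.3466 × 56/30.44) = 0.53. Success on the primary endpoint would then be about 0.53² × 0.65 = 18% and 0.53² × 0.50 = 14%, not 65% and 50%. This also stands, so the hazard ratios are illustrations. The direction follows from the formula without these durations.

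**PFS2.** A reader might extend the point to PFS2. Its definition counts death without clearly tying it to the later sequence, so a never-starter who dies can have an event. What remains there is only a label.

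**Limited consequence.** TTF2 is one of ten secondary items. The primary endpoint and OS are unaffected, and no stated decision rests on TTF2.

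**Conclusion.** The point holds as a defect in the stated TTF2 event. The definition, the ITT rule and the primary-endpoint rule do not fit together: the same patient is in the TTF2 analysis, cannot have its event, and is a failure on the primary endpoint. If the arms differ in the share starting drug 2, as the trial hypothesizes, the comparison is tilted towards the sequence that fewer patients complete. Confidence in the wording and the direction is high, the direction being shown for equal durations and censoring in the two arms.

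The size is conditional on the assumed start rates, the assumed durations and the unstated censoring date. It runs from small (about 1.05 with 80% versus 70% starting and censoring when drug 1 stops) to large (about 1.48 with 65% versus 50% starting and follow-up to cutoff). A reader might infer that TTF2 will point the opposite way from the primary endpoint. The protocol supports only that it could, since a real difference in treatment durations might offset or add to the tilt. As a secondary endpoint with an inexpensive remedy, this should be corrected but does not threaten the primary conclusion.

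**What to change.** Define TTF2 as the time from randomization to failure of the treatment sequence. The event is discontinuation of the second treatment for any reason or, for patients who never start it, permanent discontinuation of the first treatment, or death if earlier. Say that this follows the rule already used for the primary endpoint, and state how patients still between treatments at data cutoff are censored.

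The cost is the wording of one definition. The dates are already needed for TTF1 and OS, and the sample size does not change. Aligning the TTF2 objective label, which speaks of the second treatment line, with the from-randomization definition is optional wording. PFS2 needs no change on this account.
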